5.3.3.9 Cytokines

Any values expressed as $<\text{x}$ or $>\text{x}$ will be imputed as a value of x for the summary tables and for calculating changes from baseline. The actual value will be displayed in the listings.

5.3.4 Safety

5.3.4.1 Duration of Exposure

The duration of exposure will be calculated as

Duration of exposure (days) = Treatment stop date – treatment start date + 1

5.3.4.2 Treatment-Emergent Adverse Events

An adverse event (AE) will be classified as 'treatment-emergent' if the onset date/time was on or after the start date/time of study treatment. Where dates or times are missing or partially missing, AEs will be assumed to be treatment-emergent, unless there is clear evidence (through comparison of partial dates/times, see [Section 7.3.2](#)) to suggest that the AE started prior to dosing.

AEs will be classified into the following study phases based on the onset date/time of the AE after any imputations:

- Pre-Treatment Phase: All AEs with onset date/time prior to the first dose of randomized study treatment
- Treatment Phase: All AEs with onset date/time at the time of or after the first dose of randomized study treatment (Day 1) up to and including the date of the last dose of treatment received.
- Follow-up Phase: All AEs with onset date after the date of the last dose of treatment received.

For participants who complete 14 days of dosing per protocol the Treatment Phase will be from Day 1 to Day 14 and the Follow-up Phase will be from Day 15 to Day 42. In all cases the day will be assumed to start at 00:00 hours and end at 23:59 hours. Adverse events occurring in both the Treatment Phase and Follow-up Phase are classified as treatment emergent.

The onset phase of all AEs will be included in the relevant data listings.

5.3.4.3 Hematology Differentials

The database allows the white blood cell differential results (neutrophils, lymphocytes, monocytes, eosinophils and basophils) to be entered on to the CRF as either absolute values or relative values (percentage of white blood cells). If both absolute and relative values are provided in the lab report then the expectation is that the absolute values will be entered, and the relative values marked as 'Not done'.

In order to summarize all differential values together, all relative values will be converted to absolute values as follows:

Absolute value = (Relative value (%)) / 100 x White Blood Cell Count

The units for the absolute value will be the same as for the white blood cell count ($\times 10^3/\mu\text{L}$).

6 Sample Size

This is a pilot study designed to give an initial evaluation of the efficacy and safety of EDP1815 in treating Covid-19 and in evaluating multiple endpoints for clinical relevance and sensitivity, while informing the sample size for future studies. A formal power calculation was not performed, and the number of participants was selected based on feasibility.

Based on this sample size, [Table 8](#) below indicates the expected size of a 95% confidence interval for the difference between the treatments based on possible observed sample variation and drop-out rates, both for the initial recruitment of 60 participants and the possible extended recruitment to 100 participants.

Table 8 Estimated Size of Confidence Intervals for the Primary Endpoint

Participants providing at least one post-baseline S/F ratio	SD of Change from Baseline in S/F ratio	95% Confidence Interval Half-width for Treatment Difference
60 (0% drop-out)	50	25.8
	100	51.7
	150	77.5
56 (7% drop out)	50	26.8
	100	53.6
	150	80.4
52 (13% drop out)	50	27.9
	100	55.7
	150	83.6
100 (extended recruitment, 0% drop-out)	50	19.8
	100	39.7
	150	59.5
92 (extended recruitment, 8% drop out)	50	20.7
	100	41.4
	150	62.1
84 (extended recruitment, 16% drop out)	50	21.7
	100	43.4
	150	65.1

Confidence interval calculated based on the assumption that the mean change from baseline in trough S/F ratio follows a t-distribution and the two treatment groups having a common standard deviation.

Example: If all participants provided at least one valid post-baseline S/F measurement (0% drop out), the difference between the treatments was found to be 50 and the common standard deviation was 100 then the 95% confidence interval for treatment difference would be $50 \pm 51.7 = (-1.7, 101.7)$ with 60 participants or $50 \pm 39.7 = (10.3, 89.7)$ with 100 participants.

7 General Considerations

7.1 Analysis Populations

7.1.1 Enrolled Population

All participants who sign the informed consent form (ICF) will be included in the enrolled population.

7.1.2 Intention to Treat (ITT) Population

All participants randomly assigned to a study treatment group will be included in the ITT population.

Participants will be analyzed according to the study treatment group to which they were randomized.

7.1.3 Safety Population

All participants randomly assigned to a study treatment group who take at least one dose of study medication will be included in the Safety population.

Participants will be analyzed according to the intervention they received.

If a participant takes both placebo and EDP1815, due to an error in dosing, they will be assigned to the EDP1815 treatment group for all analyses using the Safety population.

7.2 Covariates and Subgroups

The following covariates will be considered as possible prognostic factors for inclusion in the analysis models described in [Section 7.2](#):

- Age ≥ 60 years (yes, no)
- Gender (male, female)
- Race (Non-Hispanic/Latino white, non-white or Hispanic/Latino)
- Baseline WHO OSCI score (4, 5)
- Time since onset of symptom at Baseline (days)
- Presence of obesity: BMI $\geq 30 \text{ kg/m}^2$ (yes, no)
- Current type 1 diabetes (yes, no)
- Current type 2 diabetes (yes, no)
- Current hypertension (yes, no)
- Other current chronic cardiovascular disease (yes, no)
- Current chronic respiratory disease (yes, no)
- Active cancer, excluding skin basal cell carcinoma or localized squamous cell carcinoma (yes, no)
- Smoking status (current smoker, not current smoker)
- Neutrophils $> 8.0 \times 10^3/\mu\text{L}$
- C-Reactive protein (CRP) $> 40 \text{ mg/dL}$

Other covariates may also be considered if emerging research into COVID-19 suggests other possible prognostic factors for outcome that can be determined from the data captured on the CRF.

Prior to database lock, the inferential primary analysis model described in [Section 9.2.2](#) will be examined on the blinded data in order to determine which baseline factors may have a prognostic effect on the efficacy endpoints. Covariates will be selected for inclusion in the model using forward stepwise selection procedure with a 5% level of significance applied for both the selection and deselection of variables from the model.

Where applicable, the baseline value of the endpoint will be automatically fitted first, regardless of significance before additional covariates are considered. A maximum of 3 covariates, in addition to the

baseline value where applicable, may be selected for each model in order to avoid over-parameterization and a reduction in the efficiency of treatment estimates.

If, during the study, a new treatment is approved for use in COVID-19 and becomes part of the standard of care for hospitalized participants at the study site(s), additional sensitivity analyses will be performed using covariates defined by use of this treatment.

- For ANCOVA analyses of trough S/F ratio
 - New SOC covariate: 'yes' if taken at any time before Day 14, 'no' otherwise
- For ANOVA analyses of S/F ratio at Day X
 - New SOC covariate: 'yes' if taken prior to Day X, 'no' otherwise
- For time-to-event analyses
 - New SOC covariate will be fitted as a time-dependent covariate with value 'yes' at time t if taken prior to time t, 'no' otherwise.

Note that the purpose of this sensitivity analysis is to account for any biases to the endpoints caused by a standard of care treatment that was available to later participants but not to those first entered. Any new medication that becomes standard of care and is available for use by all participants before Day 14 will not meet the criteria for performing this sensitivity analysis.

Subgroup analyses based on use of any new SOC medication may also be performed, depending on results seen from the sensitivity analyses using this covariate.

In addition to the covariates mentioned above, other baseline biomarkers will be examined for a prognostic effect on treatment response as part of the exploratory analysis. These will be fitted as continuous variables in the model and include the following:

- CRP (mg/dL)
- Neutrophils ($10^3/\mu\text{L}$)
- IL-6 (pg/mL)
- Ferritin (ng/mL)
- D-dimer (ng/mL)
- Neutrophil/Lymphocyte ratio (fraction of 1)
- Lactate Dehydrogenase (LDH) (IU/L)
- Troponin I (ng/mL)

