9.1. Sample Size Determination

60 participants will be randomly assigned to EDP1815 or matching placebo in a 1:1 ratio.

This is a pilot study designed to give an initial evaluation of the efficacy and safety of EDP1815 in treating Covid-19 and in evaluating multiple endpoints for clinical relevance and sensitivity, while informing the sample size for future studies. A formal power calculation was not performed and the number of participants was selected based on feasibility.

Based on this sample size, the table below indicates the expected size of a 95% confidence interval for the difference between the treatments based on possible observed sample variation and drop-out rates.

Table 4: Estimated Size of Confidence Intervals of Treatment Difference in Change from Baseline in Trough S/F Ratio

Subjects providing at least one post-baseline S/F ratio	SD of Change from Baseline in S/F ratio	95% Confidence Interval Half-width for Treatment Difference
60 (0% drop-out)	50	25.8
	100	51.7
	150	77.5
56 (7% drop out)	50	26.8
	100	53.6
	150	80.4
52 (13% drop out)	50	27.9
	100	55.7
	150	83.6

Confidence interval calculated based on the assumption that the mean change from baseline in trough S/F ratio follows a t-distribution and the two treatment groups having a common standard deviation.

Example: if all subjects provided at least one valid post-baseline S/F measurement (0% drop out), the difference between the treatments was found to be 50 and the common standard deviation was 100 then the 95% confidence interval for treatment difference would be $50 \pm 51.7 = (-1.17, 101.7)$.

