5.3.2 Demographic and Background Data

5.3.2.1 Age

Age (years) will not be recalculated using year of birth but will be taken directly from the CRF.

If participants aged >65 years are allowed to be entered into the study, then age (years) will be categorized as follows:

- 18-65 years
- 66-75 years
- >75 years

In addition, for age as a prognostic marker for COVID-19, a further categorization will be performed as follows:

- 18-59 years
- ≥ 60 years

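### Age, BMI, neutrophils and CRP are offered to the primary-model covariate selection only as two-category variables, which costs some precision and some chance of selection

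*SAP*

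**What the plan says.** SAP 7.2 states: "The following covariates will be considered as possible prognostic factors for inclusion in the analysis models". The list that follows includes age at 60 years, BMI at 30 kg/m², neutrophils at 8.0 ×10³/µL and CRP at 40 mg/dL, each as a two-category term. SAP 5.3.2.1 shows that the age split was made for this purpose: "for age as a prognostic marker for COVID-19, a further categorization will be performed", with 18-59 against 60 and over.

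Three places show that the plan also accepts finer forms:
- The same list in SAP 7.2 keeps time since symptom onset in days, with no cut.
- At the end of SAP 7.2, CRP and neutrophils appear again among the exploratory biomarkers: "These will be fitted as continuous variables in the model and include the following".
- Protocol 9.4.1 names age and BMI as covariates to be examined and gives no cut-points. It does not name CRP or neutrophils.

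SAP 7.2 and 9.1.1.2 set the selection rule: forward stepwise at 5% on blinded data, with at most three covariates beyond baseline S/F ratio, which is always fitted. The stated reason for the cap is to protect the efficiency of the treatment estimates. SAP 9.1.1.2 applies the same approach to the Cox and the Fine and Gray models. Neither document gives a reason for the cut-points.

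**The concern.** A two-category version of a measured variable uses the same single degree of freedom as a linear term but carries less information if the effect is graded. With about 60 participants and three places to fill, each place should carry as much prognostic information as it can.

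Two things are at stake. If a cut variable is selected, more residual variance is left and the interval for the treatment difference is wider than it need be. And a truly prognostic variable is less likely to pass the 5% test when cut, so it may not be selected at all. The age cut is the clearest case, because 60 lies near the top of the 18-65 range to which enrolment is first limited.

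**Working it through.** **Inputs from the documents.** Protocol 9.1: "60 participants will be randomly assigned to EDP1815 or matching placebo in a 1:1 ratio". The worked example in SAP section 6 supposes that "the common standard deviation was 100". SAP Table 8 "indicates the expected size of a 95% confidence interval for the difference between the treatments". Protocol 5.1 sets the age range at 18-65, with over-65s only after DMC approval.

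**Assumptions.** The documents give neither the distributions of the four variables nor the share of variance each explains (R²). Both are assumed below and shown over a range.

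**Step 1: reproduce the plan's figure.** Half-width = t(0.975, N−2) × SD × √(4/N). For N=60 and SD 100 this is 2.0017 × 100 × 0.2582 = 51.7, as stated. All 18 entries of SAP Table 8 reproduce to rounding.

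**Step 2: information kept after a cut.** If the covariate acts linearly, the share of its explained variance that survives is the squared correlation between the variable and its indicator. For a normal variable with a share p above the cut z, that is φ(z)²/[p(1−p)]:

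| Share above cut | Kept | Lost |
|---|---|---|
| 50% | 64% | 36% |
| 30% | 58% | 42% |
| 20% | 49% | 51% |
| 10% | 34% | 66% |
| 5% | 22% | 78% |

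The median split is the best case, hence the floor of about 36%. The loss reaches half only when fewer than about 21%, or more than about 79%, of participants are above the cut. For a uniform variable the share kept is 3p(1−p).

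**Step 3: the four variables, under assumed distributions.**
- Age, uniform on 18-65: p = 6/48 = 12.5%; kept 3 × 0.125 × 0.875 = 33%; lost 67%. Truncated normal, mean 45-60 and SD 10-15: 51-81% lost. If over-65s are admitted (range to 90): 34-73% lost.
- BMI, normal, mean 28-34 and SD 5-7: 36-50% lost, mostly 36-44%.
- Neutrophils, log-normal, median 4-7 and log-SD 0.4-1.0: 37-80% lost.
- CRP, log-normal, median 5-15 mg/dL and log-SD 0.4-1.0: 55-100% lost, with 0 to 10 of 60 participants above 40 mg/dL.

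**Step 4: effect on the interval.** Half-width = t(0.975, 57) × 100 × √(4/60) × √(1 − R² × share kept). Here 100 is the SD after baseline S/F, and R² is what the covariate adds beyond it. The percentages compare with the continuous form.

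| Share kept | R²=0.05 | Wider by | R²=0.10 | Wider by |
|---|---|---|---|---|
| 100% (continuous) | 50.4 | | 49.1 | |
| 64% | 50.9 | 1.0% | 50.0 | 2.0% |
| 50% | 51.1 | 1.3% | 50.4 | 2.7% |
| 33% (uniform age) | 51.3 | 1.8% | 50.8 | 3.7% |
| 25% | 51.4 | 2.0% | 51.1 | 4.1% |

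A much stronger covariate would matter more: at R²=0.30 with half kept, 47.7 against 43.3.

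**Step 5: effect on selection.** Take uniform age, tested alone at 5% with n=60. The noncentrality is √[60R²/(1−R²)], and the chance of selection is about Φ(noncentrality − 2.00).
- R²=0.10: continuous √(6/0.90) = 2.58, so about 72%. Cut: R² falls to 0.10 × 0.328 = 0.0328, √(1.968/0.9672) = 1.43, so about 28%.
- R²=0.05: continuous √(3/0.95) = 1.78, so about 41%. Cut: R² falls to 0.0164, √(0.984/0.9836) = 1.00, so about 16%.

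**Step 6: a dependency for BMI.** SAP 5.3.2.3 converts inches to centimetres by multiplying by 0.3937. The correct factor is 2.54, so heights recorded in inches come out too small by 2.54/0.3937 = 6.45. BMI is then inflated by 6.45² ≈ 42. Those participants would all be at or above 30 in the cut form and would be extreme leverage points in a linear one.

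**The case against.** The strongest defence is that little hangs on this. SAP section 6 says: "A formal power calculation was not performed, and the number of participants was selected based on feasibility". SAP section 9 labels all analyses descriptive. Baseline S/F ratio is forced in with no cut-point, so each candidate can only add to it. At a plausible R² the interval changes by a few per cent. All of this stands, and it keeps the point minor.

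The linear form is also an assumption. A real threshold effect near the cut would favour the categories, and the residual review in SAP 9.1.1.2 covers normality and constant variance, not the shape of each covariate's effect. This stands too, so the change needs an added check. The exploratory use of continuous CRP and neutrophils serves a different purpose, the search for predictors of response in SAP 9.4.2. It shows that the finer form is available, not that the plan contradicts itself.

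The defence also limits how far the point can be pushed. A reader might infer that the four variables enter the primary model. They do not: they are candidates, at most three covariates can be added, and possibly none of these four will be. A reader might also infer that half or more of the information is lost for every one. The documents give no distributions to support that. It is plausible for age while enrolment is limited to 18-65 and for CRP at 40 mg/dL, uncertain for neutrophils, and generally not met for BMI. The age figure also eases if the DMC opens recruitment to over-65s.

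What the defence does not supply is a reason for the cut-points, or an advantage that they bring to the adjustment.

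**Conclusion.** The point holds as a minor one about efficiency. All four variables reach the blinded selection only in two-category form, although the same list accepts a continuous candidate. For a normal covariate acting linearly the loss is at least about 36% of its explained variance. It is larger where few participants exceed the cut, and about 67% for age if uniform on 18-65.

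The half-width at N=60 and SD 100 is about 1-4% wider than with the continuous form, if the covariate explains 5-10% of variance beyond baseline S/F and 25-64% of that survives the cut. The chance of selection can fall by more: from about 72% to 28% for uniform age at R²=0.10. These figures rest on assumed distributions, an assumed R² and a linear effect.

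It would be wrong to infer bias. The covariates are measured at baseline and selected on blinded data, so their coding affects precision and selection, not the validity of the randomised comparison.

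**What to change.** In SAP 7.2 and 9.1.1.2, before the blinded selection is run:
- Offer age, BMI, neutrophils and CRP as continuous linear terms. Log-transform CRP if the blinded data show it to be skewed.
- Add plots of residuals against each selected covariate to the blinded review, so that the linear form is checked.
- Correct the inches-to-centimetres conversion in SAP 5.3.2.3 before BMI is used in any form.
- Keep the categories for the risk-factor table in SAP 8.4.
- Confirm the CRP unit for that table: 40 mg/dL equals 400 mg/L.

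The cost is a short SAP edit and a few extra plots. The data are already collected, each term still uses one degree of freedom, and the cap of three is unchanged. The downside is the assumed linear form, which the added plots address.

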9.4.1.1. Primary Efficacy Analysis

Change from baseline in trough S/F ratio will be analysed with an analysis of covariance (ANCOVA) model. The model will include fixed effect parameters for treatment and baseline S/F ratio together with the additional baseline covariates which were identified during the blinded review.

Least square (LS) estimates of the mean change from baseline trough S/F ratio together with the standard error and 95% confidence interval will be reported. The LS mean treatment difference and 95% confidence interval will also be presented.

Distributional assumptions underlying the model used for analysis will be examined by obtaining a normal probability plot of the residuals and a plot of the residuals versus the fitted values (i.e. checking the normality assumption and constant variance assumption of the model respectively) to gain confidence that the model assumptions are reasonable.

If during the course of the study, a newly approved medication for COVID-19 becomes part of the standard of care treatment at the investigational site, a further sensitivity analysis will be performed. A new-medication covariate (yes, no for use before Day 14) and an interaction for treatment*new medication will be included in the ANCOVA model described above.

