5.2 Randomization and Blinding

Participants will be randomly allocated, in a 1:1 ratio, to EDP1815 or matched placebo using a pre-prepared, blocked randomization list. Randomization numbers will be allocated sequentially. If more than one site is used in this study each site will be given complete blocks of randomization numbers.

The study will be fully blinded to the participants, site staff and sponsor. An independent statistics and programming group will be used to prepare all unblinded outputs for the iDMC which will be held in a secure area until the study has completed.

The Sponsor must be notified immediately (within 24 hours) if the investigational drug blind is broken. The date, time, and reason the blind was broken must be recorded on the appropriate Case Report Form (CRF).

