9.2.3 Sensitivity Analyses

A sensitivity analysis will be performed where no imputation of trough S/F ratio will be made for participants who die. Instead the lowest reading recorded prior to death will be used.

If a newly approved medication for COVID-19 becomes part of the standard of care treatment at the investigational site during the study an additional sensitivity analysis will be performed. A new medication covariate (yes, no for use before Day 14) will be fitted into the ANOCOVA model used for the main analytical approach together with its interaction with the EDP1815 treatment term.

In addition to the estimates of LS means for effect of each treatment group and their difference, the p-values for the significance of the new medication*treatment interaction will be provided.

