9.2.4 Subgroup Analyses

If the sensitivity analysis for a newly approved COVID-19 medication described in [Section 9.2.3](#) is performed and the p-value for the new medication*treatment interaction is found to be significant at the 5% level, the analysis described for the main analytical approach will be performed by use of the new medication prior to Day 14.

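### The new-standard-of-care analysis of trough S/F is motivated by when a drug became available but codes who took it, so its interaction and subgroup do not compare randomised arms (minor priority)

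*SAP*

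**What the plan says.** SAP 7.2 says the sensitivity analysis is meant to deal with bias "caused by a standard of care treatment that was available to later participants but not to those first entered". It defines when the analysis is not needed in the same terms: "Any new medication that becomes standard of care and is available for use by all participants before Day 14 will not meet the criteria". Purpose and exclusion rule are therefore both about availability.

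The variable is about use. For trough S/F, SAP 7.2 gives "New SOC covariate: 'yes' if taken at any time before Day 14, 'no' otherwise". SAP 9.2.3 repeats it ("A new medication covariate (yes, no for use before Day 14) will be fitted") and adds the interaction with treatment. Protocol 9.4.1.1 has the same definition: "A new-medication covariate (yes, no for use before Day 14".

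If the interaction is significant at the 5% level, SAP 9.2.4 says "the analysis described for the main analytical approach will be performed by use of the new medication prior to Day 14". SAP 7.2 leaves room for more: "Subgroup analyses based on use of any new SOC medication may also be performed, depending on results seen from the sensitivity analyses". No planned analysis uses availability as the covariate.

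**The concern.** Protocol 6.5 allows standard-of-care therapy at any time. SAP 5.3.3.3 defines the trough as the lowest S/F over Days 1-14, almost exactly the window in which use is coded. Nothing restricts use to the time before randomisation or before the trough. A participant can therefore become a 'yes' because of the deterioration that sets the outcome, or after it.

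When uptake follows clinical course and EDP1815 improves that course, an EDP1815 participant who takes the new drug has, on average, a worse underlying prognosis than a placebo participant who takes it. Users are then compared across arms at unequal prognosis. The interaction and the subgroup are what this analysis adds to the primary ANCOVA, and they are the parts that lose the protection of randomisation.

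**Working it through.** **1. The plan's own figure.** The documents give no figure for this analysis. SAP Table 8 gives the precision of the main contrast: half-width = t(0.975, N-2) × SD × √(4/N).
- N=60, SD 100: 2.0017 × 100 × 0.2582 = 51.7.
- N=100, SD 100: 1.9845 × 100 × 0.2 = 39.7.

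All 18 entries of Table 8 reproduce. The difference of 50 and SD of 100 used below come from the example in SAP section 6.

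**2. First illustration: uptake depends on outcome.** The SAP 9.2.3 model was fitted to simulated trials: change = treatment + baseline + covariate + treatment × covariate.
- From the documents: 1:1 allocation, N=60, difference 50 in everyone.
- Assumed: residual SD 100; baseline slope 30 per SD; drug available to the second half of enrolment; an inert new drug; no true interaction; log-odds of uptake among those with access = log(0.6/0.4) − slope × (change − average change)/100.
- 6,000 trials per row.

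| Covariate | 'No' group | 'Yes' group | Interaction | Interaction p<0.05 |
|---|---|---|---|---|
| Use, slope 0 | 49.6 | 49.8 | 0.2 | 5.0% |
| Use, slope 1 | 49.9 | 42.4 | -7.5 | 4.1% |
| Use, slope 2 | 48.8 | 33.5 | -15.2 | 3.8% |
| Use, slope 3 | 48.9 | 28.6 | -20.2 | 3.9% |
| Availability | 50.0 | 50.1 | 0.1 | 5.1% |

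Interactions are averaged before rounding. With slopes 1 to 3 the effect among users is understated by (50 − 42.4)/50 = 15% to (50 − 28.6)/50 = 43%. At N=20,000 the interactions are -8.3, -15.1 and -20.2, so this is bias and not small-sample noise.

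**3. Second illustration: uptake depends on an early reading.** Assumed: use is prompted by an early reading correlated 0.7 with outcome (thresholds -0.5, 0 and 0.5 SD), 50% of participants have access, and the new drug adds 0 to +100 S/F points. One million participants per scenario.
- Use coding, at every drug effect including zero: average difference 44-46, interaction -13 to -16, users 31-37, non-users 46-51.
- Availability coding, inert drug: average 50, interaction within 1 of zero.
- Availability coding, active drug: interaction -3 to -5 at +30, -6 to -8 at +60, -10 to -14 at +100. This is a real treatment-policy effect, because placebo participants take the drug more often (for example 25% against 18%).
- With correlations from 0.3 to 0.9, the use-coded average runs from 49 down to 40-43.

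Nobody straddles the adoption date in either illustration, so availability at entry and availability before Day 14 coincide.

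**4. Where the bias vanishes.** With a true difference of 0, the use-coded interaction in the first illustration is -0.2 to 0.8 at N=60. When use is set by a baseline factor, both codings average 49.7-50.4.

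**5. Precision at N=60, 50% access, second illustration.** Half-widths for the interaction are 110-165 (use) and 96-104 (availability). The use-coded interaction reaches p<0.05 in 2.5-5.0% of trials, a range that also includes scenarios with wider access.

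**The case against.** Use coding is consistent across both documents and evidently deliberate. A drug acts by being taken, and neither document calls the use strata randomised. All participants are recently hospitalised and on oxygen at entry, so uptake may well follow baseline indication, in which case there is no bias. This stands as a limit on size. It does not supply a reason for conditioning on a variable that treatment can change when the stated purpose is availability.

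Four stronger readings are tempting and not supported:
- *The main result is biased.* It is not: the primary ANCOVA does not contain this covariate.
- *The 9.2.4 gate will open falsely.* The expected interaction is non-zero, but at N=60 rejection stays at or below the nominal 5%.
- *The data monitoring committee would be misled.* Tables 14.2.1.2.3 and 14.2.1.2.4 are flagged for its efficacy review, but so is the unaffected primary table. Nothing shows that a decision would change.
- *Very early adoption makes the bias much larger.* If 90% have access, only 6 of 60 precede adoption. At about 13 or more randomised per month (14 × 13/30 ≈ 6), all six would have access before their Day 14, and SAP 7.2 would cancel the analysis. Figures for that case apply only under slower recruitment and are not relied on here.

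It is also fair that an availability covariate gives an average close to the primary ANCOVA, and that period is not randomised. The protocol and SAP allow enrolment to open to over-65s after the 20-participant review, so a before/after difference in effect may reflect age mix.

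**Conclusion.** The point holds at minor priority. The analysis is justified by availability and coded by use, and as coded its interaction and subgroup are non-randomised comparisons. The direction is clear if uptake follows clinical course and EDP1815 works: the effect among users is understated, and a constant effect shows a negative expected interaction. At about 50% access and the assumed correlation of 0.7, the interaction is about -13 to -16 and users show about 31-37 instead of 50. These sizes are illustrative, since the uptake model is not in the documents, and they are small beside the interaction half-widths of 110-165.

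The analysis runs only if a new drug becomes standard of care during the study. SAP section 9 labels all analyses descriptive. The Day X and time-to-event models also code use, the latter as a time-dependent covariate, but no size of bias is claimed for them.

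**What to change.** In SAP 7.2, 9.2.3 and 9.2.4 and protocol 9.4.1.1, code the trough S/F covariate 'yes' if the medication had become standard of care at the participant's site before that participant's scheduled Day 14, and 'no' otherwise. Derive it from the randomisation date and a recorded site adoption date: adoption earlier than randomisation date + 13 days, counting randomisation as Day 1. This follows the availability wording of SAP 7.2, cannot be affected by treatment, and avoids coding as 'no' those randomised just before adoption. Arms should be roughly balanced in each period, because numbers are allocated sequentially and "If more than one site is used in this study each site will be given complete blocks of randomization numbers".

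Report actual use by arm. Label any interaction or subgroup by use, including those allowed by SAP 7.2 and protocol 9.4.1.3, as a non-randomised comparison. State that:
- the average difference will be close to the primary ANCOVA;
- the treatment comparison within each period is randomised;
- a before/after difference in effect may also reflect other calendar changes, such as opening enrolment to over-65s.

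The cost is wording, two table titles and one date per site, with a definition of adoption that the SAP's own trigger already needs. Availability is an imprecise proxy for use: uptake may be partial, and participants who straddle adoption have fewer days of access. If adoption is very early or very late, one period may be too small to inform.
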